### **Study Visits 1 and 2**

At the end of each supplementation period, participants will report to SIT@Dover between 0800-1200 after an overnight 10-12h fast for their study visit (Visits 3 and 4 in Figure 1). There will be a washout period of 4 weeks between supplementations.

Both study visits will involve:

1. Anthropometric measurements.

Weight and height will be measured and used to calculate Body Mass index. Body composition will be measured using bioimpedance analysis. Blood pressure and resting heart rate will also be taken. All measurements will be taken before blood draw.

2. Diet History

A diet history will be performed at each study visit to obtain information about the usual dietary practices of participant. SIT Dietetics and Nutrition students will be engaged to assist in collecting this participant diet history information by the PI, [name].

3. Serial blood draw

Peripheral intravenous cannula will be inserted into antecubital vein for multiple blood sampling (5ml per collection). A baseline blood sample will be drawn at 0 min, after which participants will consume the beverage within 15 mins. Serial blood samples will be taken at 15, 30, 45, 60, 90, 120, 150 minutes after participant began consuming the plant protein beverage.

After each 5 ml blood sample is drawn, the cannula will be flushed with 2 ml normal saline to ensure patency until the next blood draw time. Upon the completion of the blood draw and removal of cannula, the venipuncture site and overall condition of the participant will be examined before the participant leaves the SIT study site, to ensure that the participant is no longer bleeding and can stand up without dizziness.

4. Stool samples will be collected using a gut microbiome test kit provided by AMILI. Participants will submit their second and third stool samples on Study Visit 1 and 2 respectively.

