### Study Design:

This study is a randomized crossover study to assess the amino acid concentration in the blood after the consumption of a plant protein beverage. The plant protein beverage is formulated and developed in SIT. The study will take place over a duration of 10 to 12 weeks, following the schedule depicted below in Figure 1. The study has already been approved by SIT-IRB.

[figure not shown]

Figure 1: Schematic diagram of Study Visits

For this study, 20 healthy participants will be recruited. Inclusion criteria include healthy body weight (BMI 18.5-23kg/m^2), and lack of any underlying medical conditions. Exclusion criteria include any individuals who were treated for or diagnosed with a gastrointestinal, cardiac, respiratory, circulatory, musculoskeletal, metabolic, immune, autoimmune, haematological, neurological or endocrinological disorder, and having any form of food allergy/intolerances/avoidances, in particular allergies to eggs, soya, peanuts, tree nuts, crustaceans, and gluten. Participants are not allowed to consume any nutritional supplements known to affect measures of the current study for 8 weeks of supplementation and washout periods, including probiotics, prebiotics, synbiotics and/or digestive enzymes. Participants who are unable to be weight stable defined as measured body mass deviating by 2% or more, and participants who were not willing to abstain from alcohol, nicotine, and caffeine for 12h prior to each study visit are also excluded.

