### **Data Analysis Plan**

Sample size was calculated based on a recent randomized, double-blind, multicenter crossover study. 15 healthy subjects showed 16- 26% increase in amino acid appearance in the blood following probiotic administration (Jäger et al., 2020). Assuming a drop-out rate of 20-30%, we plan to recruit 20 study subjects.

The area under the concentration vs. time curve (AUC) will be calculated for each of the 20 amino acids, as well as branched chain amino acids (BCAAs), essential amino acids (EAAs) and total amino acids, using the linear trapezoidal rule and using all available time points. AUC values will be compared between conditions via paired t-tests. A *p* value of <0.05 will be considered as statistically significant.

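### Nothing in the visible plan matches a participant's two visits on start time, fasting length or previous evening meal, so avoidable within-person variation can enter a small paired comparison

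*Combined protocol and SAP*

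**What the plan says.** The document describes its design this way: "This study is a randomized crossover study to assess the amino acid concentration in the blood". Each participant takes each supplement for 2 weeks, with a 4-week washout between, and attends a test visit at the end of each supplementation period.

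On conditions before a test visit, the section Study Visits 1 and 2 says "participants will report to SIT@Dover between 0800-1200 after an overnight 10-12h fast for their study visit". Study Design adds an exclusion for people unwilling to "abstain from alcohol, nicotine, and caffeine for 12h prior to each study visit", a 2% weight-stability criterion, and a ban on supplements that could affect the measurements. On diet, Study Visits 1 and 2 says "A diet history will be performed at each study visit to obtain information about the usual dietary practices of participant".

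On measurement and analysis, a baseline sample is followed by seven more: "Serial blood samples will be taken at 15, 30, 45, 60, 90, 120, 150 minutes after participant began consuming the plant protein beverage". The Data Analysis Plan computes AUC "using the linear trapezoidal rule and using all available time points" and then states "AUC values will be compared between conditions via paired t-tests". It mentions no baseline correction and no covariate. It plans to recruit 20, allowing for 20 to 30% drop-out.

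**The concern.** A crossover gains its precision by comparing a person with himself or herself under conditions that are otherwise alike. Here the window and fast range are limits on each visit, and no rule links the two visits of one person. One visit could begin early after a 12 h fast and a light supper, and the other late in the morning after a 10 h fast and a protein-rich meal, and both would comply.

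The stated controls do not close this gap. The 12 h abstentions, weight stability and supplement ban do not concern the last meal or the hour of the visit. The diet history describes habitual intake and does not standardise the evening before.

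What is at stake is precision. The paired t-test divides by the SD of the within-person differences, few pairs are expected, and the plan states neither that SD nor a target power. It therefore shows no reserve to absorb extra variation.

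**Working it through.** **Plan's own figure.** The Data Analysis Plan takes 15 subjects from the cited crossover study and inflates for drop-out, n = 15/(1 − d):
- d = 20%: 15/0.80 = 18.75, rounded up to 19
- d = 25%: 15/0.75 = 20
- d = 30%: 15/0.70 = 21.4, rounded up to 22

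The stated 20 lies within this range, and this point does not dispute it. Expected completers are 20 × 0.70 = 14 to 20 × 0.80 = 16.

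**How far apart the two visits may be.**
- Start time, literal ceiling: 1200 − 0800 = 4 h.
- Fasting length: 12 − 10 = 2 h.
- Last-meal clock time: an 0800 start implies a last meal between 2000 and 2200, and a 1200 start implies one between 0000 and 0200. The extremes, 2000 and 0200, are 6 h apart.
- The fast narrows the first figure. A person who always finishes eating at time T can start only between T + 10 h and T + 12 h, a spread of at most 2 h. With T = 2000 only an 0800 start fits the window; with T = 2200 starts run from 0800 to 1000.
- If the 4 h window must hold the whole session, 150 min of sampling leaves 240 − 150 = 90 min, less preparation time, so starts would differ by under about 1.5 h. The sentence speaks of reporting, which favours the literal reading.

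On every reading, fasting length and the content of the last meal remain unmatched.

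**How this reaches the test.** Write one person's difference as D = δ + (c₁ − c₂) + e. Here δ is the treatment effect, c₁ and c₂ are the effects of pre-visit conditions under the two supplements, and e is remaining error. Unmatched conditions add Var(c₁ − c₂) to Var(D). With randomised order the expected value of c₁ − c₂ is zero. Without baseline correction, a shift of Δ in the fasting level that persisted through sampling would add 150 min × Δ to that visit's AUC.

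**Illustration of scale, on assumed inputs.** The documents give an effect of 16 to 26% but no SD and no share of variance due to pre-visit conditions. Both are assumed below, as is a two-sided test at 0.05. Power is from the noncentral t with n = 15, 14 degrees of freedom and noncentrality δ√n / (SD√(1 − f)), where f is the share of Var(D) removed. For example, δ = 16, SD = 25 and f = 0.20 give an SD of 22.4, noncentrality 2.77 and power 73%.

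| Effect | Assumed SD of D | f = 0 | f = 10% | f = 20% | f = 30% |
|---|---|---|---|---|---|
| 16% | 20% | 82% | 86% | 90% | 93% |
| 16% | 25% | 64% | 68% | 73% | 79% |
| 26% | 30% | 88% | 91% | 94% | 96% |

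With a 26% effect and an SD of 20%, power is already 99.7%, so there is almost nothing to gain. The table shows only what would follow if f took these values. It is not evidence that f does.

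**The case against.** The strongest reply is that the plan already controls a good deal (overnight fast, 12 h abstentions, stable weight, no interfering supplements) and that each person is their own control. No passage shows that start time or the previous meal changes amino acid AUC after a 10 to 12 h fast. That is a general physiological premise, so the amount of added noise is unknown. This stands, and it is why no size is claimed.

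The visible text is also incomplete. Figure 1 is not shown, and the briefing and participant information sheet mentioned under Screening, Consent and Recruitment might carry meal or booking instructions. The point is therefore limited to the text that can be read.

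Flexible booking has value as well. Participants are staff and students giving up a morning, and appreciable drop-out is expected. If strict matching cost one completer of 15, the variance share removed would have to exceed 1/15 = 6.7% to break even, since 14/(1 − f) = 15 gives f = 1/15. This stands too, and it argues for matching where feasible and against making it a condition of attendance.

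Three stronger readings are tempting, and the documents support none of them:
- A reader might infer that visits will typically start 4 h apart. That is only the literal ceiling, and the fast narrows it for anyone with a regular evening meal.
- A reader might infer bias in the treatment comparison. Randomised order removes any systematic effect, though chance imbalance is possible with so few pairs.
- A reader might infer a definite loss of power or of effective pairs. Any such figure simply returns the variance share that was assumed.

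**Conclusion.** The point holds as a cheap improvement to the design. It is not an error or a contradiction in the plan. The visible text sets the window and fast for each visit alone and does not match a person's two visits on start time, fasting length or evening meal. With an unadjusted paired test on an AUC that has no stated baseline correction, and about 14 to 16 pairs, such differences can widen the SD of the within-person difference and cost precision.

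The size of that loss cannot be estimated from the documents. It would be small if pre-visit conditions contribute little, if the SD is well below 20%, or if the effect is near 26%. The conclusion assumes that pre-visit conditions have some influence on the measured concentrations, and that no matching rule sits in material not visible here. The planned number of participants is unaffected.

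**What to change.** Keep the existing reporting window and fast range, and add a matching rule inside them:
- Book each participant's second visit at about the start time of the first, for example within 30 min where feasible, with a similar fasting length.
- At both visits record the actual start time and last-meal time. At the first visit also note the evening meal, alongside the diet history.
- Give the participant that note in writing and send a reminder to repeat the meal before the second visit. The visits are about 6 weeks apart (4 weeks of washout plus 2 weeks of supplementation), so memory alone will not do.
- See a participant who cannot match all the same, and record the deviation, so that no completer is lost.

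The cost is slightly less booking flexibility and a small record-and-reminder task. No extra participants, blood samples or visits are needed.

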### **Serial Blood Samples Analysis**

Blood samples will be centrifuged at 1500xg for 15 min at 4°C. The resulting serum/plasma will be aliquoted, and the resultant plasma stored at -80°C before analysis. Blood samples will be analyzed for amino acid profile as well as for glucose and insulin profile. After analysis, the samples will be disposed.

### **Stool Samples Analysis**

A total of 3 stool samples will be collected from each participant to determine any changes in gut microbiome profile with probiotic/placebo supplementation. Stool samples will be stored in AMILI's laboratory prior to analysis and disposed post-analysis. Stool will be analyzed for microbiome diversity as well as functional pathways using shotgun metagenomic sequencing with the Illumina's DNA Library Preparation kit according to the manufacturer's recommended protocol. Differences in bacterial communities between pre-post samples from the same participants, and between groups with and without probiotic supplement after consumption of the plant-based protein will be compared. Taxonomic and functional profiles will also be generated.

### **Data Analysis Plan**

Sample size was calculated based on a recent randomized, double-blind, multicenter crossover study. 15 healthy subjects showed 16- 26% increase in amino acid appearance in the blood following probiotic administration (Jäger et al., 2020). Assuming a drop-out rate of 20-30%, we plan to recruit 20 study subjects.

The area under the concentration vs. time curve (AUC) will be calculated for each of the 20 amino acids, as well as branched chain amino acids (BCAAs), essential amino acids (EAAs) and total amino acids, using the linear trapezoidal rule and using all available time points. AUC values will be compared between conditions via paired t-tests. A *p* value of <0.05 will be considered as statistically significant.

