**Effect of Probiotics on Amino Acid Absorption- Study Protocol**

IRB Approval No.: 2022180

Date: 16/02/2023

**Aim:** This project aims to investigate the effect of probiotics on amino acid absorption after the consumption of a plant-protein beverage.

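### No AUC is named to answer the aim: 23 AUCs are each tested at an unadjusted p<0.05, so if probiotics have no effect the chance of at least one false positive is above 5%

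*Combined protocol and SAP*

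**What the plan says.** The Data Analysis Plan calculates an AUC "for each of the 20 amino acids, as well as branched chain amino acids (BCAAs), essential amino acids (EAAs) and total amino acids". It then states that "AUC values will be compared between conditions via paired t-tests", and its only decision rule is that a p "value of <0.05 will be considered as statistically significant".

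No section names a primary AUC, ranks the AUCs, adjusts for multiple tests or marks any of them as exploratory. Two places might have pointed to a primary, and neither does:

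- The aim is to "investigate the effect of probiotics on amino acid absorption after the consumption of a plant-protein beverage", with no summary measure of absorption attached.
- The sample-size rationale cites a 16–26% "increase in amino acid appearance in the blood following probiotic administration" from a previous crossover study, without tying it to a single amino acid, BCAAs, EAAs or the total.

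Glucose and insulin (Serial Blood Samples Analysis) and the microbiome measures (Stool Samples Analysis) are also unranked. They are not counted in the 23 or in any figure below.

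**The concern.** A 5% threshold applied to each of 23 outcomes does not limit the error of a conclusion that may rest on any of them. The plan has one aim, 23 candidate tests of it, and no rule connecting the two.

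A mixed result shows the difficulty. Suppose three single amino acids reach p<0.05 and the total AUC does not. The plan does not say whether absorption has then been shown to change. The headline AUC could be chosen after the results are seen, and a reader could not tell that it had been.

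If all 23 p-values are reported, they can be adjusted afterwards. A primary endpoint cannot be named credibly once the results are known.

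**Working it through.** **Inputs from the Data Analysis Plan.** 20 single amino acids plus BCAA, EAA and total; paired t-test; threshold 0.05; reference study of 15 subjects; drop-out 20–30%; 20 recruited. The plan does not state whether tests are one- or two-sided; two-sided is assumed.

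**The plan's own figure.** Inflating 15 by drop-out gives 15/(1 − 0.20) = 18.75, 15/(1 − 0.25) = 20 and 15/(1 − 0.30) = 21.4, so recruiting 20 is consistent with 15 completers. Conversely, 20 recruits leave 20 × 0.7 = 14 to 20 × 0.8 = 16. I use n = 15.

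**Number of tests.** 20 + 3 = 23.

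**Expected false positives with no effect.** 23 × 0.05 = 1.15. This holds at any correlation.

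**Independence bound.** 1 − (1 − 0.05)^23 = 1 − 0.95^23 = 0.693. The AUCs come from the same blood samples and the three summaries contain the single amino acids, so this is an upper reference only.

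**Allowing for correlation.** The documents give no correlation, so I simulated a range (40,000 trials per setting). Assumptions: 20 normally distributed paired differences with equal SDs and common correlation r; BCAA, EAA and total formed as sums of 3, 9 and all 20; paired t-tests at two-sided 0.05; no effect on any amino acid; n = 15.

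| Assumed r | At least one of 23 significant | At least one favouring probiotic | At least one of the 3 summary AUCs |
|---|---|---|---|
| 0 | 66% | 41% | 12% |
| 0.3 | 56% | 30% | 9% |
| 0.5 | 44% | 22% | 8% |
| 0.7 | 31% | 16% | 7% |
| 0.9 | 16% | 8% | 6% |
| 0.95 | 12% | 6% | 6% |

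The nominal rate is 5% for the second and fourth columns and 2.5% for the third. The total AUC tested alone stays at 4.7–5.1%. Most of the excess therefore comes from the 20 single amino acids.

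**Sensitivity.** Results for 14, 16 and 20 completers are within about 1 percentage point. Letting the SDs differ up to 11-fold between amino acids moved the rates by less than about 1.5 points. Even at r = 0.99 a repeat simulation (20,000 trials) gave about 8%. The rate falls to 5% only if all 23 differences are perfectly correlated.

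**The case against.** The best defence is that the plan never says one significant AUC would count as success. Read as 23 separate statements, each test keeps its 5%, and the any-of-23 rate matters only if a later report treats a single hit as answering the aim. The family of AUCs, the trapezoidal calculation and the test are all fixed in advance, and nothing suggests that results will be withheld. The size of the problem cannot be known without the correlations. Adjusting the single amino acids would cost real power, and an openly exploratory, unadjusted label could be just as defensible.

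Much of this is fair. The error rates apply when no AUC is affected, and no single value from the table should be quoted as the expected rate. The essential step is to name a primary and label the rest. Adjustment of the single amino acids matters when significance is to be claimed for them, and less if they are only described.

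The defence does not supply the missing link between the aim and a test. The plan does not call itself exploratory; it sets a significance threshold and sizes the study on a previously reported effect. Treating the three summary AUCs as the implied headline does not settle it either: the plan does not say so, and three unranked tests still give 6–12%.

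**Conclusion.** The concern holds. The count of 23, the unadjusted threshold and the absence of a primary endpoint follow directly from the text. That the chance of at least one false positive exceeds 5% when there is no effect needs only that the AUC differences are not perfectly correlated.

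How far it exceeds 5% is a range, not an estimate: about 12% to 66% for r between 0.95 and 0, under equal SDs, a common correlation and assumed groupings of 3, 9 and 20. Confidence is high that the gap exists and low about its size.

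It should be closed before unblinding, because it bears on the study's main conclusion and cannot be fully repaired afterwards.

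**What to change.** Add a few sentences to the Data Analysis Plan before unblinding, which the PRE-visit section places after all participants have finished their visits:

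1. Name one summary AUC, for example total or EAA according to where the team expects the effect, as the single primary endpoint at two-sided 0.05. State that only this test answers the aim and that the 5% error rate applies to this claim alone.
2. Label the other two summary AUCs and the 20 single amino acids as secondary or exploratory, with Holm or FDR control for the single amino acids.
3. If family-wise control is wanted beyond the primary, test the primary first and, only if it succeeds, run one Holm procedure over the other 22 AUCs; or split alpha between the summary and single-amino-acid branches. Use Holm for this, because FDR does not control family-wise error.

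Visits, samples and sample size do not change. There are two statistical costs, illustrated for n = 15, r = 0.5, equal SDs and an assumed standardised effect of 0.8 on each affected amino acid.

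*Stricter thresholds.* Power per affected single amino acid is 82% unadjusted. After adjustment over the 20:

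| Amino acids affected | Holm | FDR |
|---|---|---|
| 20 | 46% | 75% |
| 9 | 37% | 61% |
| 5 | 36% | 52% |

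*Dilution in a summary AUC.* With k of 20 affected, the standardised effect on the total is 0.8k/√(20 + 380 × 0.5) = 0.8k/14.49. This is 1.10, 0.50 and 0.28 for k = 20, 9 and 5, with power (noncentral t) of 98%, 43% and 17%. If the 9 affected are the EAAs, the EAA AUC has effect 7.2/√(9 + 72 × 0.5) = 1.07 and power 97%. The choice of primary therefore deserves thought.

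A Bonferroni correction across all 23, at 0.05/23 = 0.00217, would be a poor substitute. With 15 completers, the standardised difference detectable with an assumed 80% power rises from 0.78 to 1.21, and the power for 0.78 falls to about 29%.

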### **PRE-visit**

After informed consent, the study team will arrange for the participants to collect their personalized probiotics / placebo supplements and commence their supplementation period of 2 weeks before each study visit. Participants will be randomly assigned the probiotics or placebo supplementation arm using an online randomization software (<https://www.randomizer.org/>). Unblinding will only take place upon completion of all participants' study visit.

The PLA (placebo) capsules will consist of maltodextrin. The PRO (probiotics) supplements are commercially available products offered by AMILI. All study participants will complete the Lifestyle Questionnaire designed by AMILI and undergo a stool sample analysis to determine the which formulation of probiotics supplement they will receive. All participants will consume the PLA/PRO supplement capsules daily for 2 weeks.

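### The crossover is analysed by a plain paired t-test with no period term and no stated balance of sequences; a period effect would cost power and precision

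*Combined protocol and SAP*

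**What the plan says.** Study Design states that "This study is a randomized crossover study". Under PRE-visit, "Participants will be randomly assigned the probiotics or placebo supplementation arm using an online randomization software"; no allocation ratio, blocking or number per treatment order is given. Each supplementation period lasts 2 weeks, and Study Visits 1 and 2 adds that "There will be a washout period of 4 weeks between supplementations". The second visit therefore falls about 4 + 2 = 6 weeks after the first.

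The Data Analysis Plan gives the whole comparison in one sentence: "AUC values will be compared between conditions via paired t-tests". A p "value of <0.05 will be considered as statistically significant". The same test serves 20 single amino acids plus BCAAs, EAAs and the total, which makes 23 AUC comparisons. On numbers: "15 healthy subjects showed 16- 26% increase in amino acid appearance in the blood following probiotic administration", and "Assuming a drop-out rate of 20-30%, we plan to recruit 20 study subjects". No SD, power or expected period effect appears. Figure 1, the visit schematic, could not be read for this review, so the remark about sequence balance applies to the text only.

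**The concern.** A paired t-test treats all probiotic-minus-placebo differences as one sample. In a crossover they come from two groups, those who took the probiotic first and those who took placebo first. If AUC drifts between visits for any reason unrelated to treatment, the drift is subtracted from the difference in one group and added in the other.

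Two things follow. With equal orders the drift cancels from the mean but stays in the SD, so the test becomes conservative and the interval too wide. With unequal completers the drift also shifts the estimate, conditional on that split. The washout addresses carryover; it does nothing about a period effect. With so few completers expected there is little power to spare, and the weakness is shared by all 23 comparisons.

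**Working it through.** **Sample size in the plan.** The only step that can be reproduced is the drop-out inflation, N = 15/(1 − d): 15/0.80 = 18.75, so 19; 15/0.75 = 20; 15/0.70 = 21.4, so 22. The planned 20 fits. Twenty recruits leave 20 × 0.80 = 16 to 20 × 0.70 = 14 completers.

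**Inputs.** From the documents: 20 recruited, 14–16 completers, an effect of 16% (low end of the cited 16–26%) and alpha 0.05. Assumed: a two-sided test, SD of the within-participant difference 20% (also 15, 25 and 30%), and a period effect π (visit 2 minus visit 1) of 0, 5, 10 or 20%.

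**Model.** With treatment effect τ, the difference D has mean τ − π for probiotic-first and τ + π for placebo-first, with the same SD in both orders.

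- Paired test: mean of all D, N − 1 df. For equal orders the expected sample variance of D is SD² + π² × N/(N − 1). At 8:8, SD 20 and π = 10 this is 400 + 100 × 16/15 = 506.7, an SD of 22.5 in place of 20.
- Shift of the paired estimate, given the split: π × (placebo-first − probiotic-first)/N.
- Adjusted test: average of the two sequence means, pooled within-sequence SD, N − 2 df. It is free of π. Relative to equal orders its variance is multiplied by N²/(4·n1·n2).

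Power and type I error come from simulation, 200,000 runs per split (60,000 per split for averages over splits).

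**8:8 completers, SD 20, effect 16**

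| π (%) | Paired power (%) | Adjusted power (%) | Paired type I error (%) | Paired 95% CI half-width (points) |
|---|---|---|---|---|
| 0 | 85 | about 84.5 | 5.0 | 10.5 |
| 5 | 83 | about 84.5 | 4.4 | 10.8 |
| 10 | 78 | about 84.5 | 2.9 | 11.8 |
| 20 | 56 | about 84.5 | 0.6 | 15.1 |

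The adjusted half-width is 10.5 throughout.

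**Other SDs, 8:8, π = 10, paired vs adjusted power:** 94 vs 98% (SD 15), 60 vs 66% (SD 25), 47 vs 51% (SD 30).

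**15 completers, averaged over the possible splits (SD 20, effect 16)**

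| Allocation | Test | π = 0 | 5 | 10 | 20 |
|---|---|---|---|---|---|
| 10:10 list, random drop-out | paired | 82 | 80 | 74 | 52 |
| | adjusted | 81 | 81 | 81 | 81 |
| Simple randomisation | paired | 82 | 80 | 73 | 52 |
| | adjusted | 79 | 79 | 79 | 79 |

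Under simple randomisation the averaged type I error of the paired test is 5.0–5.1% for every π.

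**Particular splits from a 10:10 list with 5 random drop-outs, π = 10, SD 20**

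| Split | Probability | Shift (points) | Paired power, by direction | Adjusted power | Paired type I error |
|---|---|---|---|---|---|
| 8:7 | 70% | 10 × 1/15 = 0.7 | 71 or 78% | 81% | 3.0% |
| 9:6 | 27% | 10 × 3/15 = 2.0 | 63 or 85% | 80% | 4.1% |
| 10:5 | 3.3% | 10 × 5/15 = 3.3 | 54 or 90% | 77% | 6.3% |

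**Check on another scale.** Set the effect so that the paired test has 80% power with no period effect, and take 8:8. At period effects of 0.25, 0.5 and 1.0 SD of the difference, paired power is 78, 72 and 49%; adjusted power stays at about 80%.

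**The case against.** The planned test is valid. Averaged over simple randomisation it is unbiased with 5% type I error, with balanced orders it errs on the conservative side, and with no period effect nothing is lost. The documents give neither a period effect nor an SD, so every power figure rests on assumption. The most striking one (56% at a 20% period effect) needs a drift larger than the treatment effect it is set against; at 5% the balanced gap is only about 1 point. At the top of the cited range, 26%, the loss nearly disappears: 99.5 vs 99.8% at 8:8 with a 10% period effect. The standard fast, the morning visit window, the weight-stability rule and the 12-hour abstinence rule all limit drift. Adjustment can also cost power: under simple randomisation with no period effect it loses about 3 points (82 to 79%).

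All of this stands, and it fixes the weight of the point. It does not remove it. The size of a period effect cannot be known before the data are in, the design rules limit drift without excluding it, and the wider interval remains even where power is ample (11.8 vs 10.5 points at a 10% period effect). The cost of adjusting without balance is the reason to make both changes together.

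**Conclusion.** The concern holds. For a two-period crossover the plan specifies no period term, and its readable text does not promise balanced sequences. The dependable harm is lost power and precision if a period effect exists; systematic bias is not claimed. Under an SD of 20%, a 16% effect and 8:8 completers, the gain from adjusting is about 1 point of power at a 5% period effect, about 6 at 10% and about 28 at 20%. The conditional shift in the likely unequal splits (8:7 or 9:6) is 0.7 to 2.0 points at a 10% period effect. The omission is certain; whether a loss will occur is not. This should be changed because it is cheap, but the trial does not fail without it.

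**What to change.** Make two changes together.

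1. State that participants are randomised to sequence (PRO–PLA or PLA–PRO) from a balanced 10:10 list.
2. Replace the paired t-test with a linear mixed model for each AUC, with treatment, period and sequence as fixed effects and participant as random. Report the treatment difference with its 95% CI. A two-sample t-test between sequences on the within-participant period differences gives the same answer for complete pairs. With 20–30% drop-out expected, the plan should name one of the two, because only the mixed model can use participants with a single visit.

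Cost: wording and a list; no extra participants, visits or samples. With balanced completers the price is one degree of freedom (8:8, no period effect: 84.9% paired, 84.5% adjusted). With unequal completers the variance factor is 225/(4 × 56) = 1.00 at 8:7, 225/(4 × 54) = 1.04 at 9:6 and 225/(4 × 50) = 1.125 at 10:5. With no period effect that costs about 0.6, 2 and 5 points of power.
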